7.4.2.2 Dose Modifications

There will be no dose escalations or reductions of nivolumab allowed.

Nivolumab infusion can be interrupted and/or the IV infusion rate can be reduced. This information will be retrieved from CRF dosing pages.

The following will be summarized:

- Number of subjects with at least one infusion with IV rate reduced along with the reason of the rate reduction
- Number of subjects with at least one dose infusion interrupted along with the reason for the interruptions and number of infusions interrupted per subject

A by subject listing of study drug administered will be provided. A batch listing number will be also provided.

[REDACTED]

7.5 Efficacy

7.5.1 Overall Efficacy Analysis

Unless otherwise specified, all efficacy analyses will be performed for all treated subjects.

7.5.2 Primary Analysis

7.5.2.1 Statistical Hypotheses

Let Y_i be the response indicator for the i^{th} subject. Define $\pi_g = \Pr(Y_i = 1 | g_i = g)$ as the underlying probability of response for group g for the experimental treatment and R_g as the assumed probability of response for group g within the (historical) control population. Transformation to the logit scale is applied for modeling purposes. Let θ_g be the mean log odds treatment effect, i.e.

$$\theta_g = \log(\pi_g/(1-\pi_g)) - \log(R_g/(1-R_g)).$$

Thus, θ_g is the logistic regression coefficient for the treatment within tumor group g . The primary analysis is a set of group specific tests of $\theta_g > 0$ (equivalently, $\pi_g > R_g$) meaning that the treatment is better than the assumed control rate within that group. Thus, the following hypotheses are tested for each tumor group g :

$$H0g : \theta_g \leq 0,$$

$$H1g : \theta_g > 0.$$

The assumed control ORRs (R_g) vary by group and for each tumor group are provided in [Table 7.5-1](#).

Table 7.5-1: Historical Control ORRs

Group Index g	Tumor Type	Assumed Control ORR (R_g)
1	Anal Cancer (squamous cell histology)	15%
2	Biliary Tract Cancer (includes nonresectable disease), intrahepatic or extrahepatic cholangiocarcinoma, gallbladder cancer, and ampullary carcinoma	10%
3	Carcinoid after SSAs (Ki67 less than 20%)	7.5%
4	Squamous Cell Cancer of the Cervix (exocervix), Squamous Cell Cancer of the Vagina	20%
5	Endometrial Cancer (after primary treatment including RT). Subjects with tumors > 10% estrogen receptor positive pathology in the primary tumor are excluded.	20%
6	Non-squamous Cell Cancer of the Head and Neck (including Cancer of the Salivary Gland, Adenoid Cystic Carcinoma)	10%
7	Histiocytoses (including Erdheim Chester Disease [macrophage disorder], Langerhans Cell Histiocytosis [LCH, dendritic cell disorder])	15%
8	Lynch Syndrome Associated Cancers (excluding HNPCC)	12.5%
9	Medullary Thyroid Cancer (after TKI [vandetanib or cabozantinib])	20%
10	Merkel Cell Carcinoma (includes unresectable disease)	15%
11	Mesothelioma	10%
12	Nasopharyngeal Carcinoma	17.5%
13	Neuroendocrine Tumors (poorly differentiated, Ki67 > 20%)	10%
14	Neuroendocrine Tumors (well to moderately differentiated) after SSAs or everolimus, including insulinomas	15%
15	Non-Lung Small Cell Carcinoma (includes Small Cell Carcinoma of the ovary or pulmonary or hypercalcemic type)	10%
16	Penile Cancer	15%
17	Rare Women's Cancers: Clear Cell (> 50% clear cell by pathology)	5%

Group Index g	Tumor Type	Assumed Control ORR (R _g)
18	Soft-Tissue Sarcoma: Liposarcoma, Leiomyosarcoma, Malignant Peripheral Nerve Sheath Tumor, NF-1	10%
19	Testicular Cancer (chemotherapy resistant disease or relapsed within 2 years of primary therapy)	10%
20	Thymic Carcinoma or Invasive Thymoma	10%
21	Thyroid Cancer (papillary or follicular), after failing RAI and approved kinase inhibition [lenvatinib]	15%
22	Thyroid Cancer: anaplastic first line. In BRAF V600e positive subjects, investigators may administer nivolumab after vemurafenib.	5%
23	Uterine Sarcoma (excluding endometrial stromal sarcoma)	15%
24	Vulvar Cancer (post vulvectomy, cisplatin and radiotherapy)	15%
25	Adenoid Cystic Carcinoma	10%

7.5.2.2 Final Efficacy Analyses

The primary endpoint of this trial is ORR. ORR is defined as the number of participants with a best overall response of confirmed CR or PR divided by the number of all treated participants. Best overall response is defined as the best response designation, as determined by investigator, recorded between the date of first dose and the date of objectively documented progression per tumor-specific response criteria or the date of subsequent therapy, whichever occurs first. For participants without documented progression or subsequent therapy, all available response designations will contribute to the BOR determination. For subjects who continue treatment beyond progression, the BOR will be determined based on response assessments up to the time of initial RECIST 1.1 progression. Tumor assessments will occur at Week 8, Week 16, week28 and then every 12 weeks until disease progression. Once a group is stopped for futility, the group will not be re-opened for further enrollment.

A final analysis for the study will occur at least 28 weeks after the last subject of the study's first treatment. Separate final analyses will be conducted for each cohort. The final analysis for each group declares success if the Bayesian posterior probability that the treatment effect in that group (treatment compared to historical control) is above 80%. Formally:

$$Pr(\pi_g > R_g) > 0.80$$

7.5.2.3 Trial Update Efficacy Analyses

Trial update analyses will be conducted at most every 4 weeks, and includes accruing ORR data information for all subjects into the modeling framework. At each analysis, the groups will be evaluated for early stopping for futility or success by comparing posterior quantities for the ORR to pre-specified early stopping criteria based on the hierarchical model. The design will limit the maximum number of subjects per group to 25 subjects. Available resources will be used more effectively by enrolling subjects in groups that offer greater promise of efficacy. The trial update analysis subject population will be used for efficacy analyses using the hierarchical model. The all treated subjects population will be used for supporting efficacy displays.

Early Futility: If there a sufficiently low probability (20%) that the ORR in a group exceeds the historical rate R_g by at least 10%, then the group will stop enrollment early for futility. Formally, enrollment will stop early for futility if:

$$Pr(\pi g > Rg + 0.10) < 0.20$$

A group is only eligible for early stopping for futility once a minimum of 5 subjects have had the opportunity to complete 28 weeks of follow-up for ORR, i.e. up to 28 weeks after the date of first dose, in that group.

Early Success: If there a sufficiently high probability (95%) that the ORR in a group exceeds the historical rate R_g , then the group may stop enrollment early for success. Formally, enrollment may stop early for success if:

$$Pr(\pi g > Rg) > 0.95$$

A group is only eligible for early stopping for success once a minimum of 8 subjects have had the opportunity to complete 28 weeks of follow-up for ORR, i.e. up to 28 weeks after the date of first dose, in that group.

A summary of the hierarchical model analysis will be provided. For each group the following measures will be reported; the total number of evaluable subjects, the protocol-specified historical rate (R_g), the observed ORR, the estimated mean ORR and 95% credible interval (based on the posterior 2.5% and 97.5% percentiles), the posterior probability that ORR exceeds its corresponding R_g , and the posterior probability that ORR exceeds its corresponding R_g by at least 10%. Enrollment decisions and final analysis decisions based on the protocol-specified decision rules will be provided.

A summary of BOR (CR, PR, SD, progression) will be provided for each tumor group in order to support the model-based analyses for ORR.

7.5.2.4 Pause Rule

The Bayesian hierarchical model incorporates information from all cohorts into each analysis, however the primary driver of the analysis for each cohort is the data from that specific cohort. Thus, it is important that enough data is available in each cohort where possible. To minimize the possibility of excessive enrollment imbalance between the groups, enrollment may be paused in cohort at any time where 12 or more patients have enrolled, but have not had, yet, an opportunity to complete their 28 week evaluation visit (dropouts are not included in this calculation if they have no post-baseline tumor assessment). A pause will be lifted when a trial update occurs and the following conditions apply:

- At most 3 subjects have not had an opportunity to complete 28 weeks of follow-up or have discontinued due to disease progression.
- Neither early success or early futility criteria has been met for a group.

In addition, based on considerations such as emerging external data, cohorts may be paused by Sponsor decision in consultation with Steering Committee.

7.5.3 Secondary Efficacy Analyses

7.5.3.1 Duration of Response

DOOR is defined as the time from first documented response (CR or PR) to the date of the first documented tumor progression as determined by investigator or death due to any cause, whichever occurs first. Participants who start subsequent therapy without a prior reported progression will be censored at the last evaluable tumor assessments prior to initiation of the subsequent anticancer therapy. Participants who die without a reported prior progression will be considered to have progressed on the date of their death. Participants who neither progress nor die will be censored on the date of their last evaluable tumor assessment. Duration of response only applies to subjects, whose best overall response is CR or PR according to RECIST 1.1. It is defined as the time from first confirmed CR or PR until the first documented sign of disease progression (according to RECIST 1.1 criteria) or death. The following censoring rules will be applied:

Table 7.5-2: Censoring Rules for the Duration of Response Analysis

Situation	Date of Progression or Censoring	Outcome
No baseline tumor assessments and no death	First dosing date	Censored
No on study tumor assessments and no death	First dosing date	Censored
New anticancer treatment started without a prior reported progression per RECIST 1.1 or death	Date of last evaluable tumor assessment prior to or on the date of initiation of the subsequent anti-cancer therapy	Censored
Progression per RECIST 1.1 documented at scheduled or unscheduled visit and no new anticancer treatment started before	Date of the first documented tumor progression	Progressed
Subject progression free (per RECIST 1.1) and no new anticancer treatment started	Date of last tumor assessment	Censored

Death without prior progression per RECIST 1.1 and no new anticancer treatment started	Date of death	Progressed/death
----------------------------------------------------------------------------------------	---------------	------------------

The duration of response will be analyzed using Kaplan-Meier methods. Rates for Probability of Duration of Response lasting beyond 6, 9, 12 months will be computed from the Kaplan Meier estimate and corresponding 95% confidence interval will be derived based on Greenwood formula for variance derivation and on log-log transformation applied on the survivor function.

7.5.3.2 *Time to Response*

Time to response (TTR) is defined as the time from first dosing date to the date of the first confirmed response, as assessed by investigator. Summary statistics of TTR will be provided for participants who achieve PR or CR.

7.5.3.3 *Clinical Benefit Rate*

Clinical benefit rate (CBR) is defined as the number of participants with a best overall response of confirmed CR or PR, or stable disease divided by the number of all treated subjects. CBR will be provided along with the corresponding 2-sided 95% confidence intervals using the method based on the Binomial distribution.

7.5.3.4 *Overall Survival*

The OS rate at 1 year will be calculated by tumor group. OS is defined as time from the date of enrollment to the date of death. Subjects who did not die by the end of the study will be censored at the last known date alive.

Time to event distribution will be estimated using Kaplan Meier techniques. This will be done for OS. Median OS along with 95% CI will be constructed based on a log-log transformed CI for the survivor function. Rates at 1-year will be derived from the Kaplan Meier estimate and corresponding confidence interval will be derived based on Greenwood formula for variance derivation and on log-log transformation applied on the survivor function.

The status of subjects who are censored in the OS KM analysis will be tabulated for each treatment group using following categories:

- On-study: (on-treatment and not progressed, on-treatment progressed, in follow-up)
- Off-study: (lost to follow-up, withdraw consent, etc.)

7.6 *Safety*

Unless otherwise specified, the safety data will be presented by tumor group.

Whenever appropriate, analysis of all safety data will be performed by following the BMS nivolumab Core Safety SAP (version 4.0)¹ and the comprehensive specifications for the

development of data displays for tables, listings and graphs should follow the BMS nivolumab Core Safety Data Presentation Plan (DPP)².

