#### **4.4 Method of Assigning Subject Identification**

The subject number will be assigned through an interactive voice response system (IVRS) once the subject has signed the informed consent form and is registered. Every subject that signs the informed consent form must be assigned a subject number in IVRS. Specific instructions for using IVRS will be provided to the investigational site in a separate document.

The investigator or designee will register the subject for enrollment by following the enrollment procedures established by BMS. The following information is required for enrollment:

- Date that informed consent was obtained
- Date of birth (year of birth only in Germany)
- Gender at birth
- Tumor type

Once enrolled in IVRS, subjects that have met all eligibility criteria will be ready for treatment and drug vial assignment through the IVRS. The following information is required for drug vial assignment and treatment:

- Subject number
- Date of birth (year of birth only in Germany)
- Tumor Type
- Confirmation of receipt of tumor tissue in archival ( $\leq$  3 months old or new biopsy tissue) and blood samples by a central laboratory

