#### **4.5 Selection and Timing of Dose for Each Subject**

Subjects will receive treatment with nivolumab 240 mg as a 30 minute IV infusion on Day 1 of a treatment cycle every 2 weeks (14 days) for 8 doses until progression, unacceptable toxicity, withdrawal of consent, the study ends, or until Q4W dosing begins, whichever occurs first. Participants should begin study treatment within 3 calendar days of treatment assignment. Beginning with dose 9 (2 weeks following the 8th dose), subjects will receive treatment with nivolumab 480 mg as a 30 minute IV infusion every 4 weeks (28 days) ( $\pm$  3 days) until progression, unacceptable toxicity, withdrawal of consent, maximum of 24 months of treatment, or the study ends, whichever occurs first.

If required for clinic scheduling, subjects may be treated up to 3 days before or after the scheduled date, ie, at intervals of not less than 12 days from the previous dose during Q2W cycles. For Q4W dosing cycles, participants may be dosed within a  $\pm$ 3 day window. A dose given more than 3 days after the intended dose date will be considered a delay. Subsequent treatments should be based on the actual date of administration of the previous dose of drug.

No dose escalations or reductions of nivolumab are allowed. Dosing visits are not skipped, only delayed.

There are no premedications recommended for nivolumab until infusion reactions have been observed in the subject. Subjects should be carefully monitored for infusion reactions during nivolumab administration. If an acute infusion reaction is noted, subjects should be managed according to [Section 4.5.6](#).

Dose delay criteria, criteria to resume treatment, and treatment discontinuation criteria can be found in Section 4.5.1, [Section 4.5.2](#), and [Section 4.5.3](#), respectively.

Nivolumab infusions are compatible with polyvinyl chloride (PVC) or polyolefin containers and infusion sets, and glass bottles.

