**Table 5.1-1: Screening Procedural Outline CA209627**

Procedure	Screening Visit	Notes
Pregnancy Test	X	Serum or urine pregnancy testing at screening visit and repeated within 24 hours of first dose. [REDACTED]
[REDACTED]	[REDACTED]	[REDACTED] [REDACTED]
[REDACTED]	[REDACTED]	[REDACTED] [REDACTED]
IVRS/Clinical Drug Supplies		
Phone calls to IVRS	X	Phone calls must be made to IVRS as follows: 

• For subject number assignment at the time informed consent is obtained.

• Prior to dosing for study drug vial assignment (call should be made within 3 days prior to dosing).

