#### **8.3.2.4 Overall survival**

OS is defined as the time from the first dosing date to the date of death. A participant who has not died will be censored at last known date alive. OS rate at 1 year is measured as the survival rate at 1 year from Kaplan-Meier curve of OS.

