2.2 Treatment Assignment

After informed consent has been obtained and the subject's eligibility is established, the subject will be enrolled and a number will be assigned through an interactive voice response system (IVRS). Every subject that signs the informed consent form must be assigned a subject number in IVRS. Once enrolled in IVRS, subjects that have met all eligibility criteria will be ready for treatment and drug vial assignment through the IVRS.

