4.2.4 Overall Survival

OS is defined as time from the date of first dosing to the date of death. Subjects who did not die by the end of the study will be censored at the last known date alive. OS rate at 1 year is measured as the survival rate at 1 year from Kaplan-Meier curve of OS.

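### SAP 7.5.3.4 starts overall survival at enrollment, while SAP 4.2.4 and Protocol 8.3.2.4 start it at first dose; in a treated-only analysis the enrollment origin adds guaranteed survival time

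*SAP*

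**What the plan says.** Three current definitions of OS bear on the same endpoint.

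- SAP 7.5.3.4 (Overall Survival, under Secondary Efficacy Analyses): "OS is defined as time from the date of enrollment to the date of death". This section also sets out the Kaplan-Meier estimate, the median with its confidence interval, and the 1-year rate.
- SAP 4.2.4: "OS is defined as time from the date of first dosing to the date of death".
- Protocol 8.3.2.4: "OS is defined as the time from the first dosing date to the date of death".

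The analysis set is fixed in SAP 7.5.1: "Unless otherwise specified, all efficacy analyses will be performed for all treated subjects". Section 7.5.3.4 names no other set, and SAP 6.3 defines treated as having received at least one dose.

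The date of enrollment is itself not clearly fixed. SAP 2.2 puts it late: "After informed consent has been obtained and the subject's eligibility is established, the subject will be enrolled". Protocol 4.4 assigns the subject number "once the subject has signed the informed consent form and is registered", and Protocol Table 5.1-1 lists an IVRS call "For subject number assignment at the time informed consent is obtained". SAP 6.3 defines enrolled subjects by consent plus IVRS registration, with no mention of eligibility.

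**The concern.** The SAP gives one endpoint two time origins, and nothing in either document says which prevails. Two programmers working from different sections of the same SAP could report different 1-year rates and medians.

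The two origins are not equally sound. To enter the treated set, a subject must survive from enrollment to first dose. Under the enrollment origin that interval counts as survival time, yet no death can be observed in it. This is guaranteed (immortal) time, and it favours the drug. The 1-year OS rate is a named secondary endpoint, and Protocol 3.6 describes OS as a key endpoint of the study.

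**Working it through.** **1. Can the gap exceed a few days?** The only stated limit is in Protocol 4.5: "Participants should begin study treatment within 3 calendar days of treatment assignment". It runs from treatment assignment, not from enrollment. Table 5.1-1 lists two separate IVRS contacts: one at consent for the subject number, and one within 3 days before dosing for the vial. Between them, Protocol 4.4 requires confirmed central receipt of tissue and blood, and inclusion criterion 1b requires a fresh biopsy if archival tissue is more than 3 months old. The protocol's document history records removal of the 28-day screening window. SAP 2.2 therefore points to a gap of days, whereas Protocol 4.4, Table 5.1-1 and SAP 6.3 allow weeks. Inclusion criterion 1c also permits re-enrollment after screen failure with a new consent, so a treated subject may have two candidate enrollment dates.

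**2. Direction.** Let T be survival from first dose and g ≥ 0 the gap. The enrollment origin estimates Pr(g + T > 1 year), which is never below Pr(T > 1 year). With a common gap the whole curve moves right by g. This needs no survival model.

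**3. Size.** The documents give no OS assumption or precision, so there is no planned figure to reproduce. These inputs are assumptions: exponential survival from first dose, medians of 6, 8 and 12 months, and a common gap of 3 to 42 days. The conversion of 30.4375 days per month is from SAP section 8.

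S(t) = exp(−ln 2 × t / median); shift = S(12 − g) − S(12), with g in months.

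Example, median 8 months and gap 28 days: g = 28/30.4375 = 0.92 months. S(12) = exp(−0.693 × 12/8) = 35.4%. S(11.08) = exp(−0.693 × 11.08/8) = 38.3%. The shift is +2.9 points.

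| Gap | Median 6 mo (base 25.0%) | Median 8 mo (base 35.4%) | Median 12 mo (base 50.0%) | Rise in median OS |
|---|---|---|---|---|
| 3 days | +0.3 | +0.3 | +0.3 | 0.10 mo |
| 7 days | +0.7 | +0.7 | +0.7 | 0.23 mo |
| 14 days | +1.4 | +1.4 | +1.3 | 0.46 mo |
| 28 days | +2.8 | +2.9 | +2.7 | 0.92 mo |
| 42 days | +4.3 | +4.5 | +4.1 | 1.38 mo |

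Shifts are in percentage points of 1-year OS. An 18-month median (base 63.0%) gives +0.2 at 3 days and +3.4 at 42 days. If gaps vary between subjects, the shift is an average over such values.

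**4. Scale.** At the usual cohort cap of 25 subjects with no censoring, the simple 95% half-width is 1.96 × √(0.354 × 0.646 / 25) = 18.7 points.

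**The case against.** The strongest reply is that this is a drafting slip with an obvious resolution. Two of the three definitions agree, one of them in the SAP's own endpoint section, and both take the 1-year rate from the curve so defined. If enrollment follows eligibility, as SAP 2.2 says, and dosing follows within days, the shift is about 0.3 points against a half-width of about 19. The larger figures need every subject to wait 4 to 6 weeks, which no section states. The key-endpoint language in Protocol 3.6 may be template text, since the same section refers to randomized subjects in a single-arm trial. The formal status of OS is secondary and descriptive.

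Much of this stands. The size is unknown and may be negligible, and the intended origin is probably first dose. The reply does not remove the conflict, because the outlying definition sits in the section that directs the analysis. Nor does it cap the gap. The re-enrollment ambiguity matters only if the enrollment origin is kept.

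A related wording point is weaker. SAP 7.5.3.1 starts duration of response at the first documented response in one sentence and at the first confirmed response in another. If the second means the first date of a response later confirmed, the two agree, and Protocol Appendix 4 section 1.13.1 supports that reading. TTR is worded consistently but is open to the same two readings. Dates would differ only if the confirming scan were used: by at least 4 weeks (0.9 months), or by 8 or 12 weeks (1.8 or 2.8 months) between adjacent scheduled scans. This merits a clarifying sentence, no more.

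**Conclusion.** The concern holds. The SAP contradicts itself and the protocol on the OS time origin, and the version in the analysis section biases 1-year and median OS upward in a treated-only set. The contradiction and the direction follow from the documents alone. The size does not: under the assumed exponential survival it runs from about 0.3 points for a 3-day gap to about 4.5 points for a 6-week gap, with the median raised by the gap itself (0.1 to 1.4 months). For a single cohort that is small beside sampling error, but the bias has the same sign in every cohort and does not average out. The ORR success, early-success and futility rules are unaffected. It should be fixed because the rule is wrong as written and the correction is nearly free.

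**What to change.** In SAP 7.5.3.4, replace the enrollment date with the date of first dosing as the start of OS, matching SAP 4.2.4 and Protocol 8.3.2.4. First dose is a single unambiguous date, so this also settles the re-enrollment question. The cost is one phrase in the SAP. Reported OS may read slightly lower than under the enrollment origin.

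As a separate clarification, state in SAP 4.2.1, 4.2.2, 7.5.3.1 and 7.5.3.2 that duration of response starts, and TTR ends, on the date the CR or PR criteria were first met for a response later confirmed. Matching wording in Protocol 8.3.2.1 and 8.3.2.2 would need IRB/IEC approval under Protocol 9.1.1, so it should wait for the next amendment.
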